8.3. Other Efficacy Analyses

Analyses of other secondary efficacy endpoints will be performed for the ITT population. Table 6 provides a summary of analyses of other efficacy endpoints that were not included in the multiple testing strategy.

Table 6: Summary of Analyses of Other Efficacy Endpoints

| Endpoint | Missing Data Approach | Analysis Method |
|----------|-----------------------|-----------------|
| S-IGA | | |

| Endpoint | Missing Data Approach | Analysis Method |
|---|--|--------------------|
| S-IGA score of “Clear” at Weeks 2 and 4 | Multiple Imputation, Observed Data, Non-responder Imputation | CMH |
| Change from baseline in S-IGA at Weeks 2, 4, and 8 (Observed Data) | Observed Data | Summary Statistics |
| B-IGA | | |
| B-IGA success at Weeks 2 and 4 | Multiple Imputation, Observed Data, Non-responder Imputation | CMH |
| B-IGA score of “Clear” at Weeks 2, 4, and 8 | Multiple Imputation, Observed Data, Non-responder Imputation | CMH |
| B-IGA score of “Clear” or “Almost Clear” at Weeks 2, 4, and 8 | Multiple Imputation, Observed Data, Non-responder Imputation | CMH |
| Change from baseline in B-IGA at Weeks 2, 4, and 8 (Observed Data) | Observed Data | Summary Statistics |
| SI-NRS | | |
| SI-NRS Success at Weeks 1, 3, 5, 6, and 7 | Multiple Imputation, Observed Data, Non-responder Imputation | CMH |
| Change and percent change from baseline in SI-NRS at Weeks 2, 3, 4, 5, 6, 7, and 8 | Multiple Imputation and Observed Data | ANCOVA |
| WI-NRS | | |
| WI-NRS Success at Weeks 1, 3, 5, 6, and 7 | Multiple Imputation, Observed Data, Non-responder Imputation | CMH |
| Change and percent change from baseline in WI-NRS at Weeks 1, 2, 3, 4, 5, 6, 7, and 8 | Observed Data | ANCOVA |

| Endpoint | Missing Data Approach | Analysis Method |
|--|--|-----------------|
| PASI | | |
| PASI-75, at Weeks 2 and 4 and PASI-50, PASI-90, and PASI-100 at Weeks 2, 4, and 8 | Multiple Imputation, Observed Data, Non-responder Imputation | CMH |
| Change from baseline in PASI at Weeks 4 and 8 | Multiple Imputation and Observed Data | ANCOVA |
| Percent change from baseline in PASI at Weeks 2, 4, and 8 | Multiple Imputation and Observed Data | ANCOVA |
| PSSI | | |
| PSSI-75 at Weeks 2 and 4 | Multiple Imputation, Observed Data, Non-responder Imputation | CMH |
| PSSI-50, PSSI-90, and PSSI-100 at Weeks 2, 4, and 8 | Multiple Imputation, Observed Data, Non-responder Imputation | CMH |
| Change and percent change from baseline in PSSI at Weeks 2, 4, and 8 | Multiple Imputation and Observed Data | ANCOVA |
| PSD | | |
| Change and percent change from baseline in PSD total score at Weeks 2, 4, and 8 | Multiple Imputation and Observed Data | ANCOVA |
| Change and percent change from baseline in an aggregate score 3 PSD individual items dealing with Itching, Pain, and Scaling at Weeks 2 and 4. | Multiple Imputation and Observed Data | ANCOVA |
| Percent change from baseline in an aggregate score 3 PSD individual items dealing with Itching, Pain, and Scaling at Week 8 | Multiple Imputation and Observed Data | ANCOVA |
| PSD Item related to Itching (Question 1) = 0 at Weeks 2 and 4 | Multiple Imputation, Observed Data, Non-responder Imputation | CMH |
| PSD Item related to Scaling (Question | | |

| Endpoint | Missing Data Approach | Analysis Method |
|--|--|--------------------|
| 11) = 0 at Weeks 2 and 4 PSD Item related to Pain (Question 9) = 0 at Weeks 2 and 4 | | |
| Achievement of PSD Total Score=0 at Weeks 2 and 4 | Multiple Imputation, Observed Data, Non-responder Imputation | CMH |
| Change and percent change from baseline in PSD individual item scores at Week 2, 4, and 8 | Observed Data | ANCOVA |
| Scalpdex | | |
| Change and percent change from baseline in Scalpdex total score as well as the emotions, symptoms, and functioning scales at Weeks 2, 4, and 8 | Observed Data | ANCOVA |
| DLQI/CDLQI | | |
| Change and percent change from baseline in Dermatology Life Quality Index (DLQI)/ Children's DLQI (CDLQI) total scores at Weeks 2, 4, and 8 | Observed Data | ANCOVA |
| % BSA Affected by Psoriasis | | |
| Change and percent change from baseline in total body % BSA affected by psoriasis at Weeks 2, 4, and 8 | Observed Data | ANCOVA |
| Extent of Scalp Involvement | | |
| Change and percent change from baseline in percent of scalp affected by psoriasis at Weeks 2, 4, and 8 | Observed Data | Summary Statistics |

The other secondary efficacy endpoints are listed in Section 2.2.2.3. Categorical endpoints will be analyzed with methods similar to those described for the sensitivity and supplemental analyses of S-IGA and B-IGA (Section 8.1. Methods for analyses of change and percent change from baseline are described in Section 8.2.3. Table 6 identifies the methods used to handle missing data and the analysis method. The same methods used for the primary and sensitivity analyses of the primary endpoints will be used. For these other efficacy endpoints, p-values will

be presented outside of the multiple testing paradigm, and therefore should be interpreted with caution.

8.4. Subgroup Analyses of Efficacy Variables

For the co-primary endpoints, S-IGA success at Week 8 and B-IGA success at Week 8, subgroup analysis will be performed on the following using the primary estimand:

- Topical Corticosteroids – Inadequate Response, intolerance, or contraindication (Y/N)
- Topical Vitamin D derivatives -- Inadequate Response, intolerance, or contraindication (Y/N)
- Age categories (12-17, 18-64, ≥ 65)
- B-IGA at baseline (2, ≥ 3 based on data entered in EDC)
- S-IGA at baseline (3 – Moderate, 4 – Severe based on data entered in EDC)
- Gender (male, female)
- Ethnicity (Hispanic or Latino, Not Hispanic or Latino)
- Race (White, Black or African American, Others)
- Fitzpatrick score of I-III vs IV-VI
- Subjects with facial involvement
- Subjects with genitalia involvement
- Subjects with knee involvement
- Subjects with elbow involvement
- Subjects with knee or elbow involvement

The above subgroup analyses are generated with imputed data only. Methods will be similar to those used for the primary analysis of the endpoint. Baseline B-IGA/S-IGA will be removed from the CMH model for analyses by the Baseline B-IGA/S-IGA subgroups, respectively. Forest plots will be produced for the odds ratio point estimates and associated 95% confidence intervals, as well as for the and difference in proportions point estimate and associated 95% confidence intervals. The forest plots will include the overall results (point estimate and 95% confidence interval) along with vertical reference lines at 1 (odds ratio) or 0 (difference in proportions) as well as another vertical reference line at the point estimate for the overall ITT population.

9. SAFETY AND TOLERABILITY ANALYSIS

Safety will be evaluated from reported AEs, physical examinations, local tolerance assessments, changes in clinical laboratory values, changes in vital signs/weight, C-SSRS, PHQ-8, and modified PHQ-A results. No inferential statistical tests will be performed.

All safety analyses will be performed on the Safety population.

9.1. Adverse Events

An overall summary of TEAEs will be provided; this will present number and percent of subjects who reported at least 1: TEAE (including all TEAEs, TEAEs by maximum severity, and TEAEs by greatest relationship), treatment emergent serious adverse events (TESAEs), TEAE leading to discontinuation of the study drug, TEAE leading to study discontinuation, and TEAE resulting in death.

Tables including the number and percentage of subjects will be provided for the following categories:

1. TEAEs by SOC and PT
2. TEAEs by SOC, PT and Maximum Severity
3. TEAEs by SOC, PT, and Strongest Relationship to Study Drug (i.e., related vs. unrelated)
4. TEAEs by PT in descending order
5. TESAE by SOC and PT
6. TEAE leading to discontinuation of the study drug by SOC and PT
7. TEAE leading to study discontinuation by SOC and PT

In the summaries showing severity and relationship to study medication the event with the maximum severity (mild < moderate < severe) or strongest relationship (not related < related) will be reported. If a particular event is missing the severity and/or relationship, then the strongest possible severity or relationship will be assumed for analysis (severity = severe, relationship = likely).

In the AE data listings, all AEs will be displayed. AEs that are treatment emergent will be flagged and AE occurred in the application site will be flagged.

Most frequent TEAE ($\geq 1\%$) of PT will be plotted by treatment groups along with overall incidence of TEAEs and overall incidence of TESAEs.

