5.7.5. Adverse Event Reporting

The Investigator is responsible for recording all adverse events, observed by the clinic staff, or reported by the subject that occur after the first application of investigational product through 30 days after end of treatment are recorded in the subject’s medical record and the eCRF.

Serious adverse events observed by the clinic staff or reported by the subject after signing the informed consent form will be recorded.

All adverse events that meet the criteria for “serious” (i.e., SAEs) will be reported to the Sponsor via fax or e-mail to [REDACTED].com within 24 hours of becoming aware of the event, whether or not the serious events are deemed IP-related.

All serious event reporting will adhere to ICH E6: Guideline for Good Clinical Practice and ICH E2A: Clinical Safety Data Management: Definitions and Standards for Expedited Reporting. The Institutional Review Board (IRB) will be notified of the Alert Reports as per FDA, ICH and the IRB’s policies and procedures.

The Sponsor, or delegate, will be responsible for reporting SAEs to health authorities per local reporting requirements. The Investigator will be responsible for reporting events to their respective IRBs/ Ethics Review Board (ERB) in accordance with the IRB/ERB requirements.

AEs (whether serious or non-serious) and clinically significant abnormal laboratory test value(s) will be evaluated by the PI and treated and/or followed for 30 days after end of treatment until the symptoms or value(s) return to the subject’s Baseline value, or acceptable levels, as judged by the Investigator. Where appropriate, medical test(s) and/or examination(s) will be performed to document resolution of event(s).

The Investigator will review each adverse event and assess its relationship to Investigational Product (unrelated, unlikely, possibly, probably, likely). Each sign or symptom reported will be graded on the NIH NCI CTCAE toxicity grading scale 5-point severity scale (Grade 1, 2, 3, 4 and 5). The date and time of onset, time relationship to drug dosing, duration, and outcome) of each event will be noted.

The relationship of each AE to the Investigational Product will be assessed using the following definitions:

Unrelated	The AE must clearly be caused by the subject's clinical state, or the study procedure/conditions. Definitely not related to drug. Temporal sequence of an AE onset relative to administration of drug not reasonable. Another obvious cause of an AE.

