Unlikely	Time sequence is unreasonable. There is another more likely cause for an AE.
Possibly	Corresponds to what is known about the drug. Time sequence is reasonable. Could have been due to another equally, likely cause.
Probably	Is a known effect of the drug. Time sequence from taking drug is reasonable. Ceases on stopping the drug. Cannot be reasonably explained by the known characteristics of the subject's clinical state.
Likely	Is a known effect of the drug (e.g., listed in Physicians' Desk Reference, Compendium of Pharmaceuticals and Specialties, IB). Time sequence from taking drug is reasonable. Event stops upon stopping drug, event returns upon restarting drug.

The following CTCAE toxicity grading scale 5-point severity scale definitions for rating maximum severity will be used:

Grade 1	Mild; asymptomatic or mild symptoms; clinical or diagnostic observations only; intervention not indicated.
Grade 2	Moderate; minimal, local or noninvasive intervention indicated; limiting age-appropriate instrumental activities of daily living.*
Grade 3	Severe or medically significant but not immediately life-threatening; Hospitalization or prolongation of hospitalization indicated; disabling; limiting self-care activities of daily living.** Note: An experience may be severe but may not be serious, e.g., severe headache).
Grade 4	Life-threatening consequences; urgent intervention indicated.
Grade 5	Death related to AE.

Footnotes from table above:

Note: A semi-colon indicates 'or' within the description of the grade.

* Instrumental activities of daily living refer to preparing meals, shopping for groceries or clothes, using the telephone, managing money, etc.

** Self-care activities of daily living refer to bathing, dressing and undressing, feeding self, using the toilet, taking medications, and not bedridden.

AEs will be coded using the most current MedDRA® version available at the start of the study.

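### SAP 9.1 ranks maximum AE severity on three levels, but the protocol collects five CTCAE grades, so no summary table separates Grade 4 from Grade 3 events

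*SAP*

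**What the plan says.** Protocol 5.7.5 requires each reported sign or symptom to be "graded on the NIH NCI CTCAE toxicity grading scale 5-point severity scale (Grade 1, 2, 3, 4 and 5"). It introduces the grade definitions with the words "The following CTCAE toxicity grading scale 5-point severity scale definitions for rating maximum severity will be used". Grade 3 is "Severe or medically significant but not immediately life-threatening", Grade 4 is "Life-threatening consequences; urgent intervention indicated", and Grade 5 is "Death related to AE".

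SAP 9.1 plans a table of "TEAEs by SOC, PT and Maximum Severity" (Table 14.3.1.3) and includes maximum severity in the overall summary of treatment-emergent events (Table 14.3.1.1). For these summaries it takes "the event with the maximum severity (mild < moderate < severe"). For an event with severity or relationship missing, "then the strongest possible severity or relationship will be assumed for analysis (severity = severe, relationship = likely").

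Fatal events are handled separately. SAP 9.1 counts subjects with a fatal treatment-emergent event in the overall summary, and SAP 9.1.2 flags deaths in the AE listing.

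**The concern.** The analysis scale is shorter than the collection scale, and it is the top that is missing. The SAP contains no rule that places Grades 4 and 5 on its three levels, so whoever programs the tables must supply one.

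The obvious choice is to put them under severe. That conflicts with the protocol's Grade 3 definition, and it leaves a reader of the severity tables unable to tell a life-threatening event from a severe one. Safety is part of the primary objective (protocol 3.1.1). The sample size was also set partly to provide a safety database (protocol 6.1.1, SAP 3.2). The two tables concerned are the planned summaries of AE intensity.

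**Working it through.** No arithmetic beyond counting levels applies, and the plan states no figure to reproduce. The check sets the two scales side by side.

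| Protocol 5.7.5 grade | Protocol meaning | Level in SAP 9.1 |
|---|---|---|
| 1 | mild | mild |
| 2 | moderate | moderate |
| 3 | severe, not immediately life-threatening | severe |
| 4 | life-threatening | none stated |
| 5 | death | none stated |

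1. **Count of levels.** Five grades are collected and three levels are ranked: 5 − 3 = 2 grades without a level. Grades 1 to 3 match the SAP levels by the protocol's own labels, so the two without a level are the two highest.

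2. **Same quantity on both sides.** The protocol says its five definitions serve to rate maximum severity, which is what the SAP tables report. The two scales are not meant for different purposes.

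3. **Search for a mapping.** None appears in SAP 9.1, in the derived variables (6.1.7), in the AE conventions (6.1.8) or in the table list (14.1). The list gives titles only, so the levels to be displayed cannot be read from it.

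4. **The missing-value rule.** This rule shows that the SAP takes severe as the top of its scale. For relationship the rule fits, because the highest category in protocol 5.7.5 is likely. For severity it does not: severe is the third of five grades.

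5. **What other outputs show.**
   - Grade 5: counted as fatal events in the overall summary and flagged in the listing.
   - Grade 4: no count of its own. The serious-event table (14.3.1.6) is by system organ class and preferred term, without grade.
   - Grade 4 and serious are close but not identical. The protocol's footnote reads a semi-colon in a grade definition as 'or', so a need for urgent intervention is enough for Grade 4. The serious criteria in 5.7.2 ask for immediate risk of death, hospitalization or another listed criterion, and do not count emergency department visits as hospitalization. Some Grade 4 events could therefore depend on the important-medical-event judgment to enter the serious-event table.
   - Laboratory tables do not fill the gap. Protocol 6.2.2 plans shifts to the worst grade, but SAP 9.3 tabulates values below, within or above the normal range.

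**The case against.** The best reply is that little is lost. Deaths are reported twice outside the severity ranking. SAP 9.1 displays all AEs in the listings (Listing 16.2.7), and SAP 4.1 promises listings of all eCRF data, so the recorded grade should be available by subject. Being life-threatening is itself a seriousness criterion, so most Grade 4 events should reach the serious-event table; those leading to withdrawal also enter the discontinuation tables. The safety analysis is descriptive, with no inferential tests (SAP 9). All of this stands, and it limits the point to Grade 4 in summary tables.

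Three stronger readings are tempting, and the documents do not support them.

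- A reader might infer that a life-threatening event has no rank and so loses to a milder one. But the SAP's instruction is to report the maximum, and ranking such an event below a mild one would defeat it. Merging into severe is much the likelier outcome.
- A reader might infer that Grade 4 events would be visible only in the serious-event tables. The listings show otherwise.
- A reader might infer that the SAP changed a protocol-planned table and failed to record it in Section 11. The protocol's AE analysis text (6.2.1 and the closing part of 6.3.2) plans no table by severity. The severity table is a SAP addition, so its absence from Section 11 carries little weight.

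The reply does not remove the mismatch itself. The SAP states a rule that does not fit the scale collected, and no summary table recovers the distinction between Grades 3 and 4.

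**Conclusion.** The point holds as a reporting inconsistency that should be corrected. Two of the five collected grades have no level in the maximum-severity summaries. Because deaths are counted elsewhere, the practical gap is one distinction: life-threatening versus severe.

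No efficacy result, alpha level or sample size is affected. The documents give no rate of Grade 4 or 5 events, so the number of subjects concerned cannot be computed. That few are expected with a topical product is an assumption. The conclusion also assumes that the eCRF collects the five grades as the protocol requires, and that the table shells, which are not in the documents, follow the SAP text.

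**What to change.** In SAP 9.1, replace the three-level ordering with Grade 1 < 2 < 3 < 4 < 5, and show all five grades in Tables 14.3.1.1 and 14.3.1.3. Restate the missing-severity rule on that scale: keep the value now assigned (severe, that is Grade 3), drop the claim that it is the strongest possible, and flag imputed values in the tables.

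The cost is a change of SAP wording and two table shells. SAP Version 3.0 itself postdates the database lock (09-Sep-2022) and unblinding (12-Sep-2022), so this would be a further post-unblinding change and should be documented as one. It concerns descriptive tables only and has no multiplicity consequence.

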9.1.1. Adverse Events Leading to Withdrawal

A summary of incidence rates (frequencies and percentages) of TEAEs leading to withdrawal of study drug by treatment group, SOC, and preferred term will be prepared for the Safety population. Additionally, this table will be repeated for TEAEs leading to withdrawal from the study. No inferential statistical tests will be performed.

9.1.2. Deaths and Serious Adverse Events

Any deaths that occur during the study will be flagged in the AE listing.

9.2. Local Tolerability Assessments

The investigator's assessment of the application site reaction will be summarized by study visit using both categorical methods (number and percentage of subjects with each score) as well as continuous methods (e.g., mean, median). Categorical summaries will be provided for dermal response as well as other effects. No inferential statistical tests will be performed.

The subject's assessment of the application site reaction will be summarized similarly.

9.3. Clinical Laboratory Evaluations

Laboratory test results will be summarized descriptively by treatment and study visit as both observed values, change and percent change from baseline values for continuous hematology, chemistry, and urinalysis results. Categorical urinalysis results will be summarized using frequencies by study visit and treatment.

The number of subjects with clinical laboratory values below, within, or above the normal range by study visit and in relation to baseline will be tabulated for each clinical laboratory analyte by treatment group (shift table).

Abnormal results will be flagged in the listings.

9.4. Vital Signs

Descriptive summaries of observed values, changes from baseline, and percent changes from baseline will be calculated for systolic blood pressure, diastolic blood pressure, heart rate, height, weight, BMI, and oral body temperature by treatment group and visit.

The number of subjects who gain or lose $\geq 5\%$ of their baseline body weight during the course of the study, as well as subjects who gain or lose $\geq 10\%$ of their baseline body weight over the course of the study, will be summarized by treatment group. This summary will be repeated by intentionality of weight loss (intentional or unintentional, as captured on the eCRF).

Shift tables for subjects who shift from their baseline BMI category as defined in [Section 6.1.7](#) (underweight, normal, overweight, obese) to a different BMI category throughout the course of the study will be provided by treatment group and visit. This summary will be repeated by intentionality of weight loss (intentional or unintentional, as captured on the eCRF).

9.5. PHQ-8 and Modified PHQ-A

Data for PHQ-8 and modified PHQ-A will be classified using each subject's total score at a time point into a category based on the following scoring system:

- None – Minimal depression (0 to 4)
- Mild depression (5 to 9)
- Moderate depression (10 to 14)
- Moderately severe depression (15 to 19)
- Severe depression (20 to 24)

Shift tables showing the category of severity at each visit by treatment group will be presented.

9.6. C-SSRS

The C-SSRS is a questionnaire that prospectively assesses Suicidal Ideation and Suicidal Behavior. At the Screening study visit, “Baseline/Screening” version of the C-SSRS will be used. This version assesses Suicidal Ideation and Suicidal Behavior during the subject’s lifetime and during the past 6 months. For the Screening visit, “lifetime” experience of the subject with Suicidal Ideation and Suicidal Behavior will be summarized. For baseline visit, the “Since Last Visit” version will be used.

Tables will include results from the Suicidal Ideation and Suicidal Behavior sections of the C-SSRS. Frequencies and percentages of subjects with a response of “Yes” at any point on the Suicidal Ideation and Suicidal Behavior items will be summarized by study visit and treatment group.

